Marketscan: https://bwh-dope.aetion.com/projects/details/990/results/46158/result/0

Date conducted: December 15, 2019

In order to complete the initial power analysis, the dummy outcome of a 90-day gap in database enrollment will be used. This outcome is used to ensure that no information on the comparative risks of the outcomes of interest are available at this stage. Complete a 1:1 PS-matched comparative analysis using this outcome. PS should include only 3 covariates: age, sex, and combined comorbidity index. Power calculations are based on the formulas from Chow et al. (2008).

In order to complete the initial power analysis, the dummy outcome of a 90-day gap in database enrollment will be used. This outcome is used to ensure that no information on the comparative risks of the outcomes of interest are available at this stage.

Effectiveness research with Real World Data to support FDA's regulatory decision making: Protocol Template

Complete a 1:1 PS-matched comparative analysis using this outcome. PS should include only 3 covariates: age, sex, and combined comorbidity index. Power calculations are based on the formulas from Chow et al. (2008).

Reviewed by PI:	[name]	Date reviewed:	12/16/19
Reviewed by FDA:	[name]	Date reviewed:	1/2/20
Reasons for stopping			
analysis (if required):			

9. Balance Assessment after PS matching

Aetion report links (Prasugrel vs. clopidogrel):

Optum: https://bwh-dope.aetion.com/projects/details/989/results/46940/result/0
Marketscan: https://bwh-dope.aetion.com/projects/details/990/results/46941/result/0

Date conducted: 01/05/2020

After review of initial feasibility and power analyses, complete creation of the remaining covariates (see Table 1 below for list of covariates). Again, using the dummy outcome of a 90-day gap in database enrollment, complete a 1:1 PS-matched analysis. The PS should include the complete list of covariates (excluding laboratory values, which are missing in some patients).

• Provide plot of PS distributions stratified by treatment group.

Note- Please refer to Appendix B.

Report covariate balance after matching.

Note- For Table 1, please refer to Appendix B.

• Report reasons for censoring by treatment group.

  		
Overall	Referent	Exposure

Effectiveness research with Real World Data to support FDA's regulatory decision making

Dummy Outcome	0 (0.00%)	0 (0.00%)	0 (0.00%)
Death	123 (0.28%)	70 (0.32%)	53 (0.24%)

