Superiority Analysis		Non-inferiority Analysis	
Number of patients matched		Number of patients matched	
Reference	15,097	Reference	15,097
Exposed	15,097	Exposed	15,097
Risk per 1,000 patients	45.09	Risk per 1,000 patients	45.09
Desired HR from RCT	0.8	Assumed HR from RCT	1
Alpha (2-sided)	0.05	Alpha (2-sided)	0.05
		Non-inferiority margin	1.3
Number of events expected	1361.44746	Number of events expected	1361.44746
Power	0.984488939	Power	0.998013942

• Stop analyses until balance and final power assessment are reviewed by primary investigators, FDA, and assigned members of advisory board. Reviewers evaluate the results of the analyses described above in Sections 9 and 10, including numbers of patients, balance in patient characteristics, follow-up time, and reasons for censoring by treatment group, as well as overall rates of outcomes and study power.

Reviewed by PI:	[name]	Date reviewed:	12/16/19
Reviewed by FDA:	[name]	Date reviewed:	01/02/2020
Reasons for stopping			
analysis (if required):			

11. Study Confidence and Concerns

Deadline for voting on study confidence and listing concerns: 1/10/20

- If final feasibility and power analyses are reviewed and approved, proceed to the remaining protocol steps.
- All study team and advisory board members that review this protocol should at this stage provide their level of confidence for the
 success of the RWD study in the Google Form. This form also provides space for reviewers to list any concerns that they feel may
 contribute to a failure to replicate the findings of the RCT, including differences in study populations, poor measurement of study
 variables, or residual confounding. All responses will be kept confidential and individual-level results will only be shared with the
 individual respondent.

12. Register study protocol on clinicalTrials.gov

Date conducted:

• Register the study on clinicalTrials.gov and upload this document.

13. Comparative Analyses

Aetion report name:

Date conducted:

13.1 For primary analysis:

• In the PS-matched cohort from Section 9, calculate the HR for each outcome for prasugrel versus clopidogrel patients using a Cox proportional hazards model.

13.2 For secondary analyses:

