R04.89	(ICD10) Hemorrhage from other sites in respiratory passages
R04.9	(ICD10) Hemorrhage from respiratory passages, unspecified

R31	(ICD10) Hematuria
R31.0	(ICD10) Gross hematuria
R31.1	(ICD10) Benign essential microscopic hematuria
R31.2	(ICD10) Other microscopic hematuria
R31.21	
R31.29	
R31.9	(ICD10) Hematuria, unspecified
784.7	(ICD9) EPISTAXIS
784.8	(ICD9) HEMORRHAGE FROM THROAT
599.7	(ICD9) HEMATURIA
599.7	(ICD9) HEMATURIA UNSPECIFIED
599.71	(ICD9) GROSS HEMATURIA
599.72	(ICD9) MICROSCOPIC HEMATURIA
786.3	(ICD9) HEMOPTYSIS
786.3	(ICD9) HEMOPTYSIS UNSPECIFIED
786.31	(ICD9) ACUTE IDIOPATHIC PULMONARY HEMORRHAGE IN INFANTS
786.39	(ICD9) OTHER HEMOPTYSIS
The occurrence	ce of Inpatient with the following attributes: Procedure Code (Any Position) is any of: { "44.43", "43255", "0W3P8ZZ" }
44.43	(ICD9) ENDOSCOPIC CONTROL OF GASTRIC OR DUODENAL BLEEDING
77.70	(HCPCS) Esophagogastroduodenoscopy, flexible, transoral; with control of bleeding, any method / Upper
43255	gastrointestinal endoscopy including esophagus, stomach, and either the duodenum and/or jejunum as
70200	appropriate; with control of bleeding, any method
0W3P8ZZ	(ICD10) Control Bleeding in Gastrointestinal Tract, Via Natural or Artificial Opening Endoscopic

The c-statistics for the propensity score model, pre-matching was 0.744. The post-matching c-statistic was 0.538.

The c-statistics for the propensity score model, pre-matching was 0.722. The post-matching c-statistic was 0.528.

[figure not shown]

Figure 64: Post-matching propensity score overlap

[figure not shown]

Figure 64: Post-matching propensity score overlap

Table 1: Prasugrel 10 mg vs Clopidogrel 75 mg

	Unmatched									
	Opt	um	Truven				POO	LED		
Variable	Clopidogrel 75mg	Prasugrel 10mg	St. Diff.	Clopidogrel 75mg	Prasugrel 10mg	St. Diff.	Clopidogrel 75mg	Ticagrelor 90mg	St. Diff.	
Number of patients	32,556	6,872		50,795	15,187		83,351	22,059		
Age										
mean (sd)	65.63 (12.12)	58.97 (10.27)	0.59	60.92 (11.98)	56.08 (8.96)	0.46	62.76 (12.03)	56.98 (9.39)	0.54	
median [IQR]	67.00 [57.00, 75.00]	59.00 [52.00, 67.00]	0.71	60.00 [53.00, 68.00]	57.00 [50.00, 62.00]	0.28	62.73 (12.03)	57.62 (9.39)	0.47	
Age categories										
18 - 54; n (%)	6,488 (19.9%)	2,342 (34.1%)	-0.32	15,420 (30.4%)	6,296 (41.5%)	-0.23	21,908 (26.3%)	8,638 (39.2%)	-0.28	
55 - 64; n (%)	7,900 (24.3%)	2,300 (33.5%)	-0.20	19,596 (38.6%)	6,745 (44.4%)	-0.12	27,496 (33.0%)	9,045 (41.0%)	-0.17	

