,	-	-	#VALUE!	۷,225 (4.4%)	204 (1.7%)	0.10	۷,۷۷۶ (4.4%)	204 (1./%)	0.16
Metropolitan Statistical Area - Urban (any MSA) vs Rural (non-MSA)									
Urban; n (%)	-	-	#VALUE!	38,125 (75.1%)	11,909 (78.4%)	-0.08	38,125 (75.1%)	11,909 (78.4%)	-0.08
Rural; n (%)	-	-	#VALUE!	1,177 (2.3%)	269 (1.8%)	0.04	1,177 (2.3%)	269 (1.8%)	0.04

Table 1: Prasugrel 10 mg vs Clopidogrel 75 mg

N of Generic name drugs				0	0		0	0	
mean (sd)	13.63 (11.66)	11.15 (10.53)	0.22	11.00 (9.22)	9.50 (8.53)	0.17	12.03 (10.24)	10.01 (9.20)	0.21
median [IQR]	10.00 [5.00, 18.00]	8.00 [4.00, 15.00]	0.18	8.00 [5.00, 15.00]	7.00 [4.00, 12.00]	0.11	8.78 (10.24)	7.31 (9.20)	0.15
N of Brand name drugs				0	0		0	0	
mean (sd)	3.10 (4.35)	3.81 (4.42)	-0.16	3.61 (4.23)	3.98 (4.17)	-0.09	3.41 (4.28)	3.93 (4.25)	-0.12
median [IQR]	2.00 [0.00, 4.00]	2.00 [1.00, 5.00]	0	2.00 [1.00, 5.00]	2.00 [2.00, 5.00]	0	2.00 (4.28)	2.00 (4.25)	0.00

Table 1: Prasugrel 10 mg vs Clopidogrel 75 mg

			Р	S-matched						
	Ор	tum		1	iven		POO	LED		
Variable	Clopidogrel 75mg	Prasugrel 10mg	St. Diff.	Clopidogrel 75mg	Prasugrel 10mg	St. Diff.	Clopidogrel 75mg	Ticagrelor 90mg	St. Diff.	
Number of patients	6,835	6,835		15,097	15,097		21,932	21,932		
Age										
mean (sd)	58.80 (11.42)	59.02 (10.25)	-0.02	55.93 (10.14)	56.12 (8.94)	-0.02	56.82 (10.56)	57.02 (9.37)	-0.02	
median [IQR]	58.00 [51.00, 67.00]	59.00 [52.00, 67.00]	-0.09	56.00 [49.00, 62.00]	57.00 [50.00, 62.00]	-0.10	56.62 (10.56)	57.62 (9.37)	-0.10	
Age categories										
18 - 54; n (%)	2,525 (36.9%)	2,314 (33.9%)	0.06	6,689 (44.3%)	6,235 (41.3%)	0.06	9,214 (42.0%)	8,549 (39.0%)	0.06	
55 - 64; n (%)	2,191 (32.1%)	2,291 (33.5%)	-0.03	6,340 (42.0%)	6,718 (44.5%)	-0.05	8,531 (38.9%)	9,009 (41.1%)	-0.04	
65 - 74; n (%)	1,458 (21.3%)	1,861 (27.2%)	-0.14	1,285 (8.5%)	1,832 (12.1%)	-0.12	2,743 (12.5%)	3,693 (16.8%)	-0.12	
>= 75; n (%)	661 (9.7%)	369 (5.4%)	0.16	783 (5.2%)	312 (2.1%)	0.17	1,444 (6.6%)	0,681 (3.1%)	0.16	
Gender- United	(* ',	,		,	- (- ,		, (,	-, (,		
Males; n (%)	5,252 (76.8%)	5,251 (76.8%)	0.00	12,060 (79.9%)	12,032 (79.7%)	0.00	17,312 (78.9%)	17,283 (78.8%)	0.00	
Females; n (%)	1,583 (23.2%)	1,584 (23.2%)	0.00	3,037 (20.1%)	3,065 (20.3%)	0.00	4,620 (21.1%)	4,649 (21.2%)	0.00	
Region	,,,,,,,,,,,,,,,,,,,,,,,,,,,,,,,,,,,,,,,	, (,		-, (,	,,,,,,,,,,,,,,,,,,,,,,,,,,,,,,,,,,,,,,,		, (, , ,		
Northeast; n (%)	516 (7.5%)	519 (7.6%)	0.00	2,390 (15.8%)	2,403 (15.9%)	0.00	2,906 (13.3%)	2,922 (13.3%)	0.00	

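### Matching balanced mean age but not the age distribution (75 or over: 6.6% of clopidogrel vs 3.1% of prasugrel patients, SMD 0.16), and the plan neither adjusts for age afterwards nor says what to do about a failed balance check

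*Combined protocol and SAP*

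**What the plan says.** Section 9 asks for a 1:1 PS match on the full covariate list except laboratory values, using a dummy outcome, and asks that balance be reported. It does not say how age enters the PS model, and it gives no balance criterion.

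Section 10 then holds the work: "Stop analyses until balance and final power assessment are reviewed by primary investigators, FDA, and assigned members of advisory board". The reviewers are to look at balance among other things, and the sign-off has a field for reasons to stop. No threshold is given, and no step is set out for the case where balance is judged inadequate. Section 11 collects concerns, including residual confounding.

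Section 13.1 specifies the main model in these words: "In the PS-matched cohort from Section 9, calculate the HR for each outcome for prasugrel versus clopidogrel patients using a Cox proportional hazards model". No adjustment variable is named. The secondary analysis in Section 13.2 trims the unmatched cohorts and adjusts for deciles of the PS. It has no age term either.

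The pooled PS-matched age rows in Table 1 read (clopidogrel, prasugrel, standardised difference):
- 18-54: "9,214 (42.0%) 8,549 (39.0%) 0.06"
- 55-64: "8,531 (38.9%) 9,009 (41.1%) -0.04"
- 65-74: "2,743 (12.5%) 3,693 (16.8%) -0.12"
- 75 or over: "1,444 (6.6%) 0,681 (3.1%) 0.16"

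The pooled prasugrel column is headed as ticagrelor. Its counts are the sums of the two prasugrel columns (for example 369 + 312 = 681), so this is a labelling slip and does not affect the figures.

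**The concern.** Age is a strong prognostic factor for MI, stroke and death. A reader who checks only mean age sees an SMD of -0.02 and moves on. The matched clopidogrel arm nevertheless has more patients at both ends of the age range and fewer in the middle, and it has more than twice as many aged 75 or over.

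Age is the only covariate affected. No other non-laboratory mean or proportion in the matched panel has an SMD above 0.10. The pooled comorbidity index (-0.01) and frailty score (0.00) are balanced. Global summaries do not reveal the problem: for one database "The post-matching c-statistic was 0.538", and for the other it is 0.528.

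The study's result will be set beside the trial's HR of 0.81. If risk rises steeply at the oldest ages, the surplus of such patients on clopidogrel moves the HR in the direction of that target, so agreement could look better than it is. Section 13.1 applies to every outcome, so the same cohort also yields the mortality result and the two control outcomes, major bleeding and pneumonia, which are there to test validity.

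**Working it through.** **1. Reproduce the standardised differences.** The inputs are the matched counts in Table 1, with 6,835 per arm in Optum, 15,097 in MarketScan (labelled Truven there) and 21,932 pooled. With p1 for clopidogrel and p2 for prasugrel, SMD = (p1 - p2) / sqrt{[p1(1 - p1) + p2(1 - p2)] / 2}.

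| Age | Optum | SMD | MarketScan | SMD | Pooled | SMD |
|---|---|---|---|---|---|---|
| 18-54 | 2,525 vs 2,314 | 0.065 | 6,689 vs 6,235 | 0.061 | 9,214 vs 8,549 | 0.062 |
| 55-64 | 2,191 vs 2,291 | -0.031 | 6,340 vs 6,718 | -0.051 | 8,531 vs 9,009 | -0.045 |
| 65-74 | 1,458 vs 1,861 | -0.138 | 1,285 vs 1,832 | -0.119 | 2,743 vs 3,693 | -0.123 |
| 75+ | 661 vs 369 | 0.162 | 783 vs 312 | 0.167 | 1,444 vs 681 | 0.163 |

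The stated 0.16, 0.17 and 0.16 for 75 or over are reproduced. The two older bands nearly cancel: 65 or over combined is 19.1% vs 19.9% pooled, SMD -0.02. Taking the four bands as one variable, the multi-level SMD is 0.206, 0.209 and 0.204 (Optum, MarketScan, pooled).

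**2. Why the mean hides it.** The age SDs (clopidogrel vs prasugrel) are 11.42 vs 10.25, 10.14 vs 8.94 and 10.56 vs 9.37. The variance ratios are (11.42/10.25)² = 1.24, (10.14/8.94)² = 1.29 and (10.56/9.37)² = 1.27. Equal means with unequal spread would fit a PS with age as a single linear term. That is an inference, because the documents do not state the form.

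**3. Whether older comparators were scarce.** All 369 Optum and 312 MarketScan prasugrel patients aged 75 or over were matched. Before matching there were 8,522 and 7,903 clopidogrel patients of that age, about 23 and 25 per prasugrel patient. Across all bands the lowest ratio is 15,420 / 6,296 = 2.4 (MarketScan, 18-54).

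**4. Possible effect on the HR.** The pooled differences, prasugrel minus clopidogrel, are -3.0, +2.2, +4.3 and -3.5 percentage points from youngest to oldest. The documents give no age-specific hazards, so those below are assumptions. With relative hazard r in each band and no true drug effect, and ignoring censoring, apparent HR = Σ(p2·r) / Σ(p1·r).

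Worked case, r = 1, 1.5, 2.25, 3.375 (a ratio of 1.5 per band): 1.4896 / 1.5072 = 0.988.

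| Assumed gradient across the four bands | Apparent HR when the true HR is 1.00 |
|---|---|
| Near-linear: 1/1.3/1.6/1.9; 1/1.5/2/2.5; 1/2/3/4; 1/1.5/2.5/3 | 1.001; 1.001; 1.002; 1.004 |
| Constant ratio of 1.3; 1.4; 1.5 per band | 0.996; 0.993; 0.988 |
| Intermediate: 1/1.3/2/3; 1/1.25/1.75/3 | 0.986; 0.976 |
| Steep: 1/2/4/8; 1/1/1.5/3 | 0.959; 0.960 |
| Steeper at 75+: 1/1.25/1.5/4; 1/1/1.25/4 | 0.943; 0.924 |

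**5. Scale.** With Section 10's 2,274.8 expected pooled events, SE(log HR) is about 2/√2,274.8 = 0.042. The two database event counts sum to 801.47 + 1,361.45 = 2,162.9, which gives 0.043, so the choice hardly matters. A shift to 0.988 is 0.3 SE, to 0.96 about 1 SE, and to 0.924 about 1.9 SE.

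**The case against.** The strongest reply is that the consequence is small and uncertain. Mean age and the proportion aged 65 or over both agree. The near-linear gradients give shifts of at most 0.4%, slightly against prasugrel, so even the direction is not fixed. The larger shifts need steep assumed gradients. Comorbidity and frailty are balanced, so the age effect that remains after them may be shallower than a crude one. This stands, and it is why the point is not rated higher.

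The second reply is that an unadjusted Cox model is the usual analysis after PS matching, and that Section 10 gives reviewers the power to stop the work. Both are true. But the unadjusted model relies on the match having done its job, and for age it did not. The review can halt the study, yet nothing says what counts as failure or what follows. Nor does the record show a review of this table: the match carries "Date conducted: 01/05/2020", while the Section 10 reviews are dated 12/16/19 and 01/02/2020, the same dates as in Section 8. That may be only a copying slip.

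Third, counts by age band do not prove PS overlap within each band, and no re-match has been run. The ratios in step 3 of the working make a workable re-match likely, not certain.

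**Conclusion.** The concern holds and should be fixed. The imbalance is certain: it is in the plan's own table, reproduces from the counts and recurs in both databases. Neither the primary model nor, as far as the documents show, the PS-decile analysis removes it. If the deciles come from the same PS, they carry the same treatment of age.

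Its effect on the HR is probably small: close to nil if hazard rises in equal steps, about 1% if it multiplies by 1.5 per band, and 4% to 8% in prasugrel's favour only under steep gradients. These sizes rest on assumed relative hazards and ignore censoring. The imbalance would not by itself produce an HR of 0.81. The case for acting is that this is a known defect in one covariate, and it can be removed before comparative outcomes are seen. A correction made later would be open to the charge of being post hoc.

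**What to change.** Before any outcome run, and separately in each database, either refit the PS with age as the four bands or a spline, or match 1:1 on the PS within the four bands. Then repeat the Section 9 balance table. State in the plan a balance criterion that covers the age bands as well as mean age. An absolute SMD below 0.10 on every PS covariate is a common convention, though it is not in the plan. Say what is done if the criterion is not met. If the present match is kept, add age band to the primary Cox model in Section 13.1.

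The cost is one re-run of the match and Table 1 with the dummy outcome. Some pairs may be lost, probably few given at least 2.4 clopidogrel patients per prasugrel patient in every band. Balance on the other covariates must be checked again. Adding age band to the Cox model needs no new match.

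As a separate record query, confirm the Section 10 review dates, which precede the match they are meant to cover.

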4	Fibrin-specific fibrinolytic therapy less than 24 h before randomization	N/A	
5	Non-fibrin-specific fibrinolytic therapy less than 48 h before randomization	N/A	
6	Active internal bleeding or history of bleeding diathesis	Measured 180 days prior to drug initiation in any diagnosis position and inpetient or outputient setting For active internal bleading, refer to the sheet "Bleading"	Cunningham A, Stein CM, Chung CP, Daugherty JR, Smalley WE, Ray WA. An automated database case definition for serious bleeding related to oral anticoagulant use. Pharmacoepidemiol Drug Saf. 2011;20(6):560–566. doi:10.1002/pds.2109
7	Clinical findings, in the Judgment of the investigator, associated with an increased risk of bleeding	or Bleeding distribusis: ICD-9: 286.x Coagulation defects 287.x Purpura and other hemorrhagic conditions	Huybrechts KF, Gopalakrishnan C, Bartels DB, Zint K, Gurusamy VK, Landon J, et al. Safety and effectiveness of debigatran and other direct oral anticoagulants compared to warfarin in patients with atrial fibrillation. Clin Pharmacol Ther. 2019 Dec 23.
	Any of the following:		
	a) History of hemorrhagic stroke	Measured any time prior to index hospitalization in any diagnosis position, inpatient or outpatient setting Hemorrhagic stroke: ICD-9: 430.xx, 431.xx ICD-10: ICD.xx, IS1.xx,	2018;360:k119 http://dx.doi.org/10.1136/bmj.k119 Patorno, Elisabetta et al. "Empagliflozin and the Risk of Heart Failure Hospitalization In Routine Clinical Care: A First Analysis from the Empagliflozin Comparative Effectiveness and Safety (EMPRES) Study." Circulation. 2019 Apr 8. doi:
		Measured 180 days prior to drug initiation in any diagnosis position and inpatient or	10.1161/CIRCULATIONAHA.118.039177
8	b) Intracranial neoplasm, arteriovenous malformation, or aneurysm	outpatient setting Intracrantal reopiasm ICD-9: 191.x, 225.0, 225.2, 225.4 ICD-10: C71.x, D32.x, D33.x, AV matformation (of brain) ICD-9: 747.81 ICD-10: Q82.x Corobra Aneuryem ICD-9: 437.3 ICD-10: 167.1	
	c) Ischemic stroke within 3 months prior to screening	Measured 90 days prior to Index hospitalization in any position, inpatient setting, isohemic stroke:	Patorno, Elisabetta et al. "Cardiovascular outcomes associated with canagliflozin versus other non-giflozin antidiabetic drugs: population based cohort study," BMJ 2018;360:k19 http://dx.doi.org/10.1136/bmj.k119 Patorno, Elisabetta et al. "Empgliflozin and the Risk of Heart Failure Hospitalization
		ICD-9: 433.xx, 434.xx, 436.xx ICD-10: I63.xx I65.xx I66.xx	in Routine Clinical Care: A First Analysis from the Empagliflozin Comparative Effectiveness and Safety (EMPRISE) Study." Circulation. 2019 Apr 8. doi: 10.1161/CIRCULATIONAHA.118.039177
9	International normalized ratio known to be greater than 1.5 at the time of screening	N/A	
10	Platelet count of less than 100000/mm3 at the time of screening	Measured during index hospitalization in inpatient setting, any position Thrombosytopenia: ICD-10: D99, Bobd-4x, D69.5x, D69.2x, D69.3x ICD-9: 287.3x, 287.4x	
11	Anemia (hemoglobin b10 g /dL) at the time of screening	Meesured during Index hospitalization in Inpetient setting, any position ICD-9: 280.0 Iron deficiency anemia secondary to blood loss (chronic) 285.1 Acute most hemorrhaeic anemia! 285.9 (Anemia unspecified)	
11	Anemia (hemoglobin b $10\mathrm{g/dL}$) at the time of screening		

	Prior/concomitant therapy exclusion criteria		
12	One or more doses of a thienopyridine 5 d or less before PCI	Prescription for following drugs 5 days prior to Index hospitalization Clopidogrel, prasugrel, or ticlopidine	
13	Oral anticoagulation or other antiplatelet therapy that cannot be safely discontinued for the duration of the study	N/A	
	Daily treatment with nonsteroidal antiinflammatory drugs (NSAIDs) or cyclooxygenase-2 inhibitors (COX-2 inhibitors)	More than 150 days of supply out of 180 days prior to drug initiation NSAID: aspirin, ibuprofen, naproxen >> OTC cannot be captured COX-2 inhibitors: celecoxib	
	General exclusion criteria		
15		N/A	
16	Employed by Eli Lilly and Company; Ube Industries Limited, Dalichi Sankyo Co.; The TIMI Study Group; Quintiles	N/A	
17	Treatment within the last 30 d with an investigational drug or are presently enrolled in another drug or device study	N/A	
18	Previously completed or withdrawn from this study or any other study investigating prasugrel	N/A	
19	Women who are known to be pregnant, have given birth within the past 90 d, or are breast-feeding	N/A	
20		Following Index score measured 180 days prior to drug Initiation Combined comorbidity index CCI >=10	Gagne, Josh J et. al. "'A combined comorbidity score predicted mortality in elderly patients better than existing scores." J Clin Epidemiol. 2011 Jul;64(7):749-59. doi: 10.1016/j.jclinepi.2010.10.004. Sun, Jenny W et. al. "Validation of the Combined Comorbidity Index of Charlson and Elixhauser to Predict 30-Day Mortality Across ICD-9 and ICD-10." Med Care. 2018
21	Known severe hepatic dysfunction	Measured 1.80 days prior to drug initiation in any diagnosis position and inpatient or outpatient esting Liver disease 1.070.xt, 570.xx. 573.xx, 456.0x-456.2x, 576.8x, 782.4x, 789.5x 10.39 procedure codes: 39.1x, 42.91	Sep:56(9):812. doi: 10.1097/MIR.000000000000054. Patorno, Elisabeta et al. "Cardioscaular outcome associated with canagliflozin versus other non-giflozin antidiabetic drugs: population based cohort study." BMJ 2018;360:k119 http://dx.doi.org/10.1136/pmj.k119 Patorno, Elisabeta et al. "Empagliflozin and the Risk of Heart Fallure Hospitalization in Routine Clinical Care. A First Analysis from the Empagliflozin Comparative Effectiveness and Safety (EMPRISE) Study." Circulation. 2019 Apr 8. doi: 10.1161/CIRCULATIONAHA.118.039177
	Any condition associated with poor treatment compliance including alcoholism, mental illness, or drug dependence	Measured 180 days prior to drug initiation in any diagnosis position and inpatient or outpatient setting Schizophrenia: ICD-9-CM codes: 295.xx; ICD-10-CM codes: F20.xx Psycholas: ICD-9-CM codes: 290.8x, 290.9x, 297.xx, 298.xx, 780.1x; ICD-10-CM codes: F20.5x; ICD-10-CM codes: F20, F24, F23.3, F23.8, F28, F29, R44.0, R44.2, R44.3 Dalifum: ICD-9-CM codes: 290.1x, 290.3x, 294.1x, 294.8x, 311.19, 331.82; ICD-10-CM codes: F05, F01.51, F03.90, F10.231, F06.2, F06.0 Dementia: ICD-9-CM codes: 290.xx, 294.1x, 294.8x, 311.19, 331.82; ICD-10-CM codes: F03.xx, F02.80, F02.81, G31.83, Drug abuse or dependence: ICD-9-CM codes: 292.xx, 304.xx, 305.2x-305.9x, 648.3x, 760.72, 760.73, 760.75, 965.0x, 967.xx, 969.4x-969.6x, 969.72-969.79, 970.1, T07.081; ICD-IO-CM codes: Alcohol abuse or dependence: ICD-9-CM codes: 291.xx, 303.xx, 305.0x, 357.5x, 425.5x, 571.0x - 571.3x, E860.0, V11.3; ICD-IO-CM codes:	Patorno, Elisabetta et al. "Cardiovascular outcomes associated with canagliflozin versus other non-gillifozin antidiabetic drugs: population based cohort study." BMJ 2018-296-V14 b http://dx.doi.org/10.1136/bmj.dv.dv.dv.dv.dv.dv.dv.dv.dv.dv.dv.dv.dv.
23		N/A	
24	May be unable to cooperate with protocol requirements and follow-up procedures	N/A	
			•

Trial ID	pNDA14
Trial Name (with web links)	TRITON-TIMI 38
Trial Name (with pdf links)	TRITON-TIMI 38
NCT	NCT00097591
Trial category	Primary indication
Run-in period Description	
Run-in period?	?
Therapeutic Area	Cardiology/Vascular Diseases
Study batch	Antiplatelets
RCT Category	1a-Intended S with label change
Brand Name	Efient
Generic Name	prasugrel
Sponsor	Eli Lilly
Year	2009
	Primary composite endpoint of death from
Measurable endpoint	cardiovascular causes, nonfatal myocardial
I Wicasarabic Chaponic	infarction, or nonfatal stroke. The key
	safety end point was major bleeding.
Exposure	Prasugrel
Comparator	Clopidogrel
	patients with moderate-to-high-risk acute
Population	coronary syndromes with scheduled
	percutaneous coronary intervention
Trial finding	HR = 0.81 (95% CI 0.73–0.90)
Notes	
No. of Patients	13,608
Non-inferiority margin	-
Assay Sens. Outcome	
Assay Sens. Endpoint (from trial)	
Finding for potential Assay Sens.	
Outcome from trial-	
Power	0.90 to detect 20% reduction in the relative
	risk
Blinding	Double-blinded

Statistical Method	
	for the prevention of thrombotic
Approval indication	cardiovascular complications in acute
	coronary syndromes

Mortality-Dependent on data source.

1. All-cause mortality / inpatient mortality Identified using the vital status file-

Medicare

Identified using the discharge status codes-

Optum-

- 20 = EXPIRED
- 21 = EXPIRED TO BE DEFINED AT STATE LEVEL
- 22 = EXPIRED TO BE DEFINED AT STATE LEVEL
- 23 = EXPIRED TO BE DEFINED AT STATE LEVEL
- 24 = EXPIRED TO BE DEFINED AT STATE LEVEL
- 25 = EXPIRED TO BE DEFINED AT STATE LEVEL
- 26 = EXPIRED TO BE DEFINED AT STATE LEVEL
- 27 = EXPIRED TO BE DEFINED AT STATE LEVEL
- 28 = EXPIRED TO BE DEFINED AT STATE LEVEL
- 29 = EXPIRED TO BE DEFINED AT STATE LEVEL
- 40 = EXPIRED AT HOME (HOSPICE)
- 41 = EXPIRED IN A MEDICAL FACILITY (HOSPICE)
- 42 = EXPIRED PLACE UNKNOWN (HOSPICE)

Truven-

- 20 Died
- 22 Died
- 23 Died
- 24 Died
- 25 Died
- 26 Died
- 27 Died
- 28 Died
- 29 Died
- 40 Other died status or Expired at home (Hospice claims only) (depends on year)
- 41 Other died status or Expired in medical facility (Hospice claims only) (depends on year)

- 42 Other died status or Expired place unknown (Hospice claims only) (depends on year)
- 21 Died or Disch./Transf. to court/law enforcement (depends on year)

2. CV mortality

Information on CV mortality through data linkage with the National Death Index (NDI) will be available for Medicare at a later date. We will conduct secondary analyses using CV mortality at that time.

Major bleeding co	Major bleeding control outcome: 1 inpatient (any position)		
Major bleeding exclusion criteria: 1 inpatient (any position) or 2 outpatient diagnosis (separated by 7-365 days)			
562.02	(ICD9) DIVERTICULOSIS OF SMALL INTESTINE WITH HEMORRHAGE		
562.03	(ICD9) DIVERTICULITIS OF SMALL INTESTINE WITH HEMORRHAGE		
562.12	(ICD9) DIVERTICULOSIS OF COLON WITH HEMORRHAGE		
562.13	(ICD9) DIVERTICULITIS OF COLON WITH HEMORRHAGE		
568.81	(ICD9) HEMOPERITONEUM (NONTRAUMATIC)		
569.3	(ICD9) HEMORRHAGE OF RECTUM AND ANUS		
569.83	(ICD9) PERFORATION OF INTESTINE		
569.85	(ICD9) ANGIODYSPLASIA OF INTESTINE WITH HEMORRHAGE		
569.86	(ICD9) DIEULAFOY LESION (HEMORRHAGIC) OF INTESTINE		
578	(ICD9) HEMATEMESIS		
578.9	(ICD9) HEMORRHAGE OF GASTROINTESTINAL TRACT UNSPECIFIED		
423	(ICD9) HEMOPERICARDIUM		
432	(ICD9) NONTRAUMATIC EXTRADURAL HEMORRHAGE		
432.1	(ICD9) SUBDURAL HEMORRHAGE		
432.9	(ICD9) UNSPECIFIED INTRACRANIAL HEMORRHAGE		
459	(ICD9) HEMORRHAGE UNSPECIFIED		
531	(ICD9) ACUTE GASTRIC ULCER WITH HEMORRHAGE		
531	(ICD9) ACUTE GASTRIC ULCER WITH HEMORRHAGE WITHOUT OBSTRUCTION		
531.01	(ICD9) ACUTE GASTRIC ULCER WITH HEMORRHAGE WITH OBSTRUCTION		
531.2	(ICD9) ACUTE GASTRIC ULCER WITH HEMORRHAGE AND PERFORATION		
531.2	(ICD9) ACUTE GASTRIC ULCER WITH HEMORRHAGE AND PERFORATION WITHOUT OBSTRUCTION		
531.21	(ICD9) ACUTE GASTRIC ULCER WITH HEMORRHAGE AND PERFORATION WITH OBSTRUCTION		
531.4	(ICD9) CHRONIC OR UNSPECIFIED GASTRIC ULCER WITH HEMORRHAGE		
531.4	(ICD9) CHRONIC OR UNSPECIFIED GASTRIC ULCER WITH HEMORRHAGE WITHOUT OBSTRUCTION		
531.41	(ICD9) CHRONIC OR UNSPECIFIED GASTRIC ULCER WITH HEMORRHAGE WITH OBSTRUCTION		
531.6	(ICD9) CHRONIC OR UNSPECIFIED GASTRIC ULCER WITH HEMORRHAGE AND PERFORATION		
531.6	(ICD9) CHRONIC OR UNSPECIFIED GASTRIC ULCER WITH HEMORRHAGE AND PERFORATION WITHOUT OBSTRUCTION		
531.61	(ICD9) CHRONIC OR UNSPECIFIED GASTRIC ULCER WITH HEMORRHAGE AND PERFORATION WITH OBSTRUCTION		

532	(ICD9) ACUTE DUODENAL ULCER WITH HEMORRHAGE
532	(ICD9) ACUTE DUODENAL ULCER WITH HEMORRHAGE WITHOUT OBSTRUCTION
532.01	(ICD9) ACUTE DUODENAL ULCER WITH HEMORRHAGE WITH OBSTRUCTION
532.2	(ICD9) ACUTE DUODENAL ULCER WITH HEMORRHAGE AND PERFORATION
532.2	(ICD9) ACUTE DUODENAL ULCER WITH HEMORRHAGE AND PERFORATION WITHOUT OBSTRUCTION
532.21	(ICD9) ACUTE DUODENAL ULCER WITH HEMORRHAGE AND PERFORATION WITH OBSTRUCTION
532.4	(ICD9) CHRONIC OR UNSPECIFIED DUODENAL ULCER WITH HEMORRHAGE
532.4	(ICD9) CHRONIC OR UNSPECIFIED DUODENAL ULCER WITH HEMORRHAGE WITHOUT OBSTRUCTION
532.41	(ICD9) CHRONIC OR UNSPECIFIED DUODENAL ULCER WITH HEMORRHAGE WITH OBSTRUCTION
532.6	(ICD9) CHRONIC OR UNSPECIFIED DUODENAL ULCER WITH HEMORRHAGE AND PERFORATION
532.6	(ICD9) CHRONIC OR UNSPECIFIED DUODENAL ULCER WITH HEMORRHAGE AND PERFORATION WITHOUT OBSTRUCTION
532.61	(ICD9) CHRONIC OR UNSPECIFIED DUODENAL ULCER WITH HEMORRHAGE AND PERFORATION WITH OBSTRUCTION
533	(ICD9) ACUTE PEPTIC ULCER OF UNSPECIFIED SITE WITH HEMORRHAGE
533	(ICD9) ACUTE PEPTIC ULCER OF UNSPECIFIED SITE WITH HEMORRHAGE WITHOUT OBSTRUCTION
533.01	(ICD9) ACUTE PEPTIC ULCER OF UNSPECIFIED SITE WITH HEMORRHAGE WITH OBSTRUCTION
533.2	(ICD9) ACUTE PEPTIC ULCER OF UNSPECIFIED SITE WITH HEMORRHAGE AND PERFORATION
533.2	(ICD9) ACUTE PEPTIC ULCER OF UNSPECIFIED SITE WITH HEMORRHAGE AND PERFORATION WITHOUT OBSTRUCTION
533.21	(ICD9) ACUTE PEPTIC ULCER OF UNSPECIFIED SITE WITH HEMORRHAGE AND PERFORATION WITH OBSTRUCTION
533.4	(ICD9) CHRONIC OR UNSPECIFIED PEPTIC ULCER OF UNSPECIFIED SITE WITH HEMORRHAGE
533.4	(ICD9) CHRONIC OR UNSPECIFIED PEPTIC ULCER OF UNSPECIFIED SITE WITH HEMORRHAGE WITHOUT OBSTRUCTION
533.41	(ICD9) CHRONIC OR UNSPECIFIED PEPTIC ULCER OF UNSPECIFIED SITE WITH HEMORRHAGE WITH OBSTRUCTION
533.6	(ICD9) CHRONIC OR UNSPECIFIED PEPTIC ULCER OF UNSPECIFIED SITE WITH HEMORRHAGE AND PERFORATION
533.6	(ICD9) CHRONIC OR UNSPECIFIED PEPTIC ULCER OF UNSPECIFIED SITE WITH HEMORRHAGE AND PERFORATION WITHOUT OBSTRUCTION
533.61	(ICD9) CHRONIC OR UNSPECIFIED PEPTIC ULCER OF UNSPECIFIED SITE WITH HEMORRHAGE AND PERFORATION WITH OBSTRUCTION
534	(ICD9) ACUTE GASTROJEJUNAL ULCER WITH HEMORRHAGE
534	(ICD9) ACUTE GASTROJEJUNAL ULCER WITH HEMORRHAGE WITHOUT OBSTRUCTION

[figure not shown]
534.01	(ICD9) ACUTE GASTROJEJUNAL ULCER WITH HEMORRHAGE WITH OBSTRUCTION
534.2	(ICD9) ACUTE GASTROJEJUNAL ULCER WITH HEMORRHAGE AND PERFORATION
534.2	(ICD9) ACUTE GASTROJEJUNAL ULCER WITH HEMORRHAGE AND PERFORATION WITHOUT OBSTRUCTION
534.21	(ICD9) ACUTE GASTROJEJUNAL ULCER WITH HEMORRHAGE AND PERFORATION WITH OBSTRUCTION
534.4	(ICD9) CHRONIC OR UNSPECIFIED GASTROJEJUNAL ULCER WITH HEMORRHAGE
534.4	(ICD9) CHRONIC OR UNSPECIFIED GASTROJEJUNAL ULCER WITH HEMORRHAGE WITHOUT OBSTRUCTION
534.41	(ICD9) CHRONIC OR UNSPECIFIED GASTROJEJUNAL ULCER WITH HEMORRHAGE WITH OBSTRUCTION
534.6	(ICD9) CHRONIC OR UNSPECIFIED GASTROJEJUNAL ULCER WITH HEMORRHAGE AND PERFORATION
534.6	(ICD9) CHRONIC OR UNSPECIFIED GASTROJEJUNAL ULCER WITH HEMORRHAGE AND PERFORATION WITHOUT OBSTRUCTION
534.61	(ICD9) CHRONIC OR UNSPECIFIED GASTROJEJUNAL ULCER WITH HEMORRHAGE AND PERFORATION WITH OBSTRUCTION
578.1	(ICD9) BLOOD IN STOOL
719.1	(ICD9) HEMARTHROSIS
719.1	(ICD9) HEMARTHROSIS SITE UNSPECIFIED
719.11	(ICD9) HERARTHROSIS INVOLVING SHOULDER REGION
719.12	(ICD9) HEMARTHORSIS INVOLVING UPPER ARM
719.13	(ICD9) HEMARTHROSIS INVOLVING FOREARM
719.14	(ICD9) HEMARTHROSIS INVOLVING HAND
719.15	(ICD9) HEMARTHROSIS INVOLVING PELVIC REGION AND THIGH
719.16	(ICD9) HEMARTHROSIS INVOLVING LOWER LEG
719.17	(ICD9) HEMARTHROSIS INVOLVING ANKLE AND FOOT
719.18	(ICD9) HEMARTHROSIS INVOLVING OTHER SPECIFIED SITES
719.19	(ICD9) HEMARTHROSIS INVOLVING MULTIPLE SITES
430	(ICD9) SUBARACHNOID HEMORRHAGE
431	(ICD9) INTRACEREBRAL HEMORRHAGE
131.2	(ICD10) Hemopericardium, not elsewhere classified
160.00	(ICD10) Nontraumatic subarachnoid hemorrhage from unspecified carotid siphon and bifurcation
160.01	(ICD10) Nontraumatic subarachnoid hemorrhage from right carotid siphon and bifurcation
160.02	(ICD10) Nontraumatic subarachnoid hemorrhage from left carotid siphon and bifurcation
160.10	(ICD10) Nontraumatic subarachnoid hemorrhage from unspecified middle cerebral artery
160.11	(ICD10) Nontraumatic subarachnoid hemorrhage from right middle cerebral artery
160.12	(ICD10) Nontraumatic subarachnoid hemorrhage from left middle cerebral artery

-		
	160.2	(ICD10) Nontraumatic subarachnoid hemorrhage from anterior communicating artery
	160.30	(ICD10) Nontraumatic subarachnoid hemorrhage from unspecified posterior communicating artery
	160.31	(ICD10) Nontraumatic subarachnoid hemorrhage from right posterior communicating artery
	160.32	(ICD10) Nontraumatic subarachnoid hemorrhage from left posterior communicating artery
	160.4	(ICD10) Nontraumatic subarachnoid hemorrhage from basilar artery
	160.50	(ICD10) Nontraumatic subarachnoid hemorrhage from unspecified vertebral artery
	160.51	(ICD10) Nontraumatic subarachnoid hemorrhage from right vertebral artery
	160.52	(ICD10) Nontraumatic subarachnoid hemorrhage from left vertebral artery
	160.6	(ICD10) Nontraumatic subarachnoid hemorrhage from other intracranial arteries
	160.7	(ICD10) Nontraumatic subarachnoid hemorrhage from unspecified intracranial artery
	160.8	(ICD10) Other nontraumatic subarachnoid hemorrhage
	160.9	(ICD10) Nontraumatic subarachnoid hemorrhage, unspecified
	161.0	(ICD10) Nontraumatic intracerebral hemorrhage in hemisphere, subcortical
	161.1	(ICD10) Nontraumatic intracerebral hemorrhage in hemisphere, cortical
	161.2	(ICD10) Nontraumatic intracerebral hemorrhage in hemisphere, unspecified
	161.3	(ICD10) Nontraumatic intracerebral hemorrhage in brain stem
	161.4	(ICD10) Nontraumatic intracerebral hemorrhage in cerebellum
	161.5	(ICD10) Nontraumatic intracerebral hemorrhage, intraventricular
	161.6	(ICD10) Nontraumatic intracerebral hemorrhage, multiple localized
	161.8	(ICD10) Other nontraumatic intracerebral hemorrhage
	161.9	(ICD10) Nontraumatic intracerebral hemorrhage, unspecified
	162.00	(ICD10) Nontraumatic subdural hemorrhage, unspecified
	162.01	(ICD10) Nontraumatic acute subdural hemorrhage
	162.02	(ICD10) Nontraumatic subacute subdural hemorrhage
	162.03	(ICD10) Nontraumatic chronic subdural hemorrhage
	162.1	(ICD10) Nontraumatic extradural hemorrhage
	162.9	(ICD10) Nontraumatic intracranial hemorrhage, unspecified
	K25.0	(ICD10) Acute gastric ulcer with hemorrhage
	K25.2	(ICD10) Acute gastric ulcer with both hemorrhage and perforation
	K25.4	(ICD10) Chronic or unspecified gastric ulcer with hemorrhage
	K25.6	(ICD10) Chronic or unspecified gastric ulcer with both hemorrhage and perforation
	K26.0	(ICD10) Acute duodenal ulcer with hemorrhage
	K26.2	(ICD10) Acute duodenal ulcer with both hemorrhage and perforation

K26.4	(ICD10) Chronic or unspecified duodenal ulcer with hemorrhage
K26.6	(ICD10) Chronic or unspecified duodenal ulcer with both hemorrhage and perforation
K27.0	(ICD10) Acute peptic ulcer, site unspecified, with hemorrhage
K27.2	(ICD10) Acute peptic ulcer, site unspecified, with both hemorrhage and perforation
K27.4	(ICD10) Chronic or unspecified peptic ulcer, site unspecified, with hemorrhage
K27.6	(ICD10) Chronic or unspecified peptic ulcer, site unspecified, with both hemorrhage and perforation
K28.0	(ICD10) Acute gastrojejunal ulcer with hemorrhage
K28.2	(ICD10) Acute gastrojejunal ulcer with both hemorrhage and perforation
K28.4	(ICD10) Chronic or unspecified gastrojejunal ulcer with hemorrhage
K28.6	(ICD10) Chronic or unspecified gastrojejunal ulcer with both hemorrhage and perforation
K55.21	(ICD10) Angiodysplasia of colon with hemorrhage
K56.60	(ICD10) Unspecified intestinal obstruction
K57.01	(ICD10) Diverticulitis of small intestine with perforation and abscess with bleeding
K57.11	(ICD10) Diverticulosis of small intestine without perforation or abscess with bleeding
K57.13	(ICD10) Diverticulitis of small intestine without perforation or abscess with bleeding
K57.21	(ICD10) Diverticulitis of large intestine with perforation and abscess with bleeding
K57.31	(ICD10) Diverticulosis of large intestine without perforation or abscess with bleeding
